- a. Does your YNHH privilege delineation currently include the **specific procedure** that you will perform? Yes No
- b. Will you be using any new equipment or equipment that you have not used in the past for this procedure? Yes No
- c. Will a novel approach using existing equipment be applied? Yes No

If you answered "no" to question 4a, or "yes" to question 4b or c, please contact the YNHH Department of Physician Services ([name]) for prior approval before commencing with your research protocol.

IMPORTANT REMINDER ABOUT RESEARCH AT YNHH

Please note that if this protocol includes Yale-New Haven Hospital patients, including patients at the HRU, the Principal Investigator and any co-investigators who are physicians or mid-level practitioners (includes PAs, APRNs, psychologists and speech pathologists) who may have direct patient contact with patients on YNHH premises must have medical staff appointment and appropriate clinical privileges at YNHH. If you are uncertain whether the study personnel meet the criteria, please telephone the Physician Services Department at [contact]. **By submitting this protocol as a PI, you attest that you and any co-investigator who may have patient contact has a medical staff appointment and appropriate clinical privileges at YNHH.**

SECTION I: RESEARCH PLAN

1. **Statement of Purpose:** State the scientific aim(s) of the study, or the hypotheses to be tested.

We propose to examine, in 172 women newly diagnosed with Stage I-III breast cancer who are not practicing the dietary and lifestyle guidelines, and who will receive neoadjuvant or adjuvant chemotherapy as part of their treatment, the effect of a 1-year dietary and physical activity guidelines intervention vs. usual care on the breast cancer outcomes described below. Women will be enrolled either before beginning chemotherapy or following the first chemotherapy infusion but prior to the second chemotherapy infusion (Time 0). Follow up visits will occur post chemotherapy (Time 1), at one-year post-diagnosis (Time 2), at two years post-diagnosis (Time 3) and at five years post-diagnosis.

Primary Endpoints: Adherence to Breast Cancer Treatments

Aim 1a: Chemotherapy completion rates (dose amount, number of dose reductions and dose delays)

Aim 1b: Adherence to endocrine therapy in women taking tamoxifen or Aromatase Inhibitors (AIs) at 12- and 24-months after enrollment

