*Dual Energy X-Ray Absorptiometry (DEXA) scans: DEXA scans will be used to assess body fat percentage, LBM and bone mineral density at baseline, post-chemotherapy, 1- and 2-years. The DEXA measurements will be made with a Hologic scanner (Hologic 4500 with a "Discovery" upgrade, Hologic Inc, Waltham, Mass). All DEXA scans will be evaluated by a radiologist who will be blinded to the intervention group of the participant, and a quality control phantom will be used daily for calibration. Women of childbearing potential will be required to complete a pregnancy test prior to the DEXA scan. Women who are pregnant or intend to get pregnant during the 2-year study time period are excluded from the study. Women who can get pregnant will have a pregnancy test prior to each DEXA scan, if the pregnancy test is positive the woman will not be able to enroll in the study or, if already enrolled, will no

longer be able to participate in the study. However, the data collected prior to pregnancy will be included in the study. (Yale in-person visit only)

Quality of Life (QOL): Women will complete the PROMIS questionnaire to assess physical, emotional, social, and functional well-being as well as fatigue and overall quality of life (74) ,at baseline, post-chemotherapy, 1- 2- and 5-years. (86) They will also complete the EORTLC QLQ- CIPN20 to assess peripheral neuropathy (77), the Breast Cancer Prevention Trial Symptoms Checklist

Work History: Women will complete a questionnaire on work history which can be impacted by chemotherapy (87).

Medical Usage: At the Year 5 timepoint, the following data will be abstracted from the EPIC EMR: breast cancer recurrence, second primary breast cancer, weight, health care utilization.

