1. "In the past month, how often did you take your medications as the doctor prescribed?" Possible responses are all of the time (100%), nearly all of the time (90%), most of the time (75%), about half the time (50%), or less than half the time (<50%). Nonadherence is defined as 75% of the time or less.
2. "In the past month, how often did you forget to take 1 or more of your prescribed medications?" Possible responses were never, once in the past month, 2 to 3 times in the past month, once per week, several times per week, and nearly every day. Nonadherence is defined as forgetting to take prescribed medications once per week or more.
3. "In the past month, how often did you decide to skip 1 or more of your prescribed medications?" Possible responses were the same as for question 2. Nonadherence is defined as deciding to skip medications once per week or more. The first will be the primary measure of non-adherence. (73,74) (75) If women switch AIs or from AI to tamoxifen, we will capture this, but classify them as having continued endocrine therapy and therefore adherent. All women who discontinue tamoxifen or AI will

be asked to indicate their rationale(s) via an interview-administered questionnaire. Note: The self-reported adherence questionnaire will be completed independent of whether a urine sample is collected.

Beliefs about Medication Questionnaire: Participants will complete the Beliefs about Medication questionnaire at baseline, 1 2 and 5 years. (78) We will also collect additional information about factors potentially influencing adherence at those 3 time points including: out-of-pocket costs, number and type of other prescriptions (from EPIC), degree to which the patient believes in the drug's efficacy, recurrence risk perception, and social support. These factors as well as age, education, smoking, comorbidities, chemotherapy, and any endocrine therapy side effects they experience during the trial will be examined in relation to endocrine therapy adherence.

COVID-19 Questionnaire

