Relative dose intensity will be calculated using the methods described by Longo et al [24]. The primary endpoint, RDI will be analyzed both as a continuous scale using the t test, and as a dichotomized outcome using 85% or 95% cut-off for Mantel-Haensel chi-square test controlling for stratification factors. In addition, group differences in chemotherapy completion rates will be analyzed with binary logistic regression analysis; whether or not having dose reduction during the period of chemotherapy treatment (the period between T0 and T1) will be the dichotomized dependent variable. The outcome of endocrine therapy adherence will be assessed at the 2 and 5-year follow ups (as most, if not all, participants prescribed endocrine therapy will have been taking it for at least 1 year at the 2-year visit, allowing us to assess adherence to endocrine therapy). The primary endocrine therapy outcome will be adherence to endocrine therapy assessed via the electronic medical records. Note: the assessment for the primary outcome of endocrine therapy adherence was changed from the initial assessment (urinary metabolites) as the COVID pandemic limited our ability to collect urine samples.

Secondary assessments of endocrine therapy will be:

a) Urinary AI level. An undetectable level will classify the participant as nonadherent to AIs.

b) Responses to the following questions:

(1) “In the past month, how often did you take your medications as the doctor prescribed?” Possible responses are all of the time (100%), nearly all of the time (90%), most of the time (75%), about half the time (50%), or less than half the time (<50%). Nonadherence is defined as 75% of the time or less.

(2) “In the past month, how often did you forget to take 1 or more of your prescribed medications?”

Possible responses were never, once in the past month, 2 to 3 times in the past month, once per week, several times per week, and nearly every day. Nonadherence is defined as forgetting to take prescribed medications once per week or more.

(3) “In the past month, how often did you decide to skip 1 or more of your prescribed medications?”

Possible responses were the same as for question 2. Nonadherence is defined as deciding to skip medications once per week or more. The first will be the primary measure of non-adherence. (73,74).

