Participants who report that they have discontinued taking tamoxifen or AI will also be classified as nonadherent to endocrine therapy. For patients who may be lost to follow-up, we will obtain prescription refill data as an endpoint of adherence to endocrine therapy. For the endocrine

therapy aim, we will compare the crude adherence rates using simple logistic regression. Multivariate logistic regression will serve as supportive analyses including covariate adjustments – which are similar to the primary analysis above.

The secondary aims will be performed using Mixed Model Repeated Measures analysis incorporating Analysis of Covariance, where each woman's changes in outcome (follow-up measure – baseline) will be modeled as a function of treatment and time with a covariate included for the baseline value. Prior to fitting models, we will perform exploratory data analyses focusing on the distributions of biological markers by time and intervention group, assessing the appropriateness of log-transformation.

All hypotheses will be tested according to the intention-to-treat philosophy in which all randomized participants will be grouped according to their intervention assignment at randomization, regardless of compliance or adherence to the study. Statistical significance will be defined as $p < 0.05$, 2-sided. Since we have multiple outcomes, we will consider using a Bonferroni correction.

Age, menopausal status, race/ethnicity, BMI at diagnosis, disease stage, type of surgery, type of chemotherapy, radiation therapy, hormone receptor status, endocrine therapy, reconstructive surgery, type 2 diabetes, and smoking status will be examined as covariates. We will explore effect modification by menopausal status at diagnosis, hormone receptor status, and endocrine therapy.

We will further explore intervention effects on study endpoints by stratifying by adherence to diet and physical activity guidelines with a four-level category (e.g., met diet recommendations, met physical activity, met both diet and physical activity recommendations, or met neither recommendation). This analysis will allow us to better understand the role of diet vs. exercise on study endpoints.

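### The self-report discontinuation rule scores a woman whose endocrine drug was stopped because of recurrence or a second primary breast cancer as nonadherent

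*Combined protocol and SAP*

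**What the plan says.** Endocrine therapy adherence is a primary aim (Section I, item 1, Aim 1b). Item 12 sets the main measure: "The primary endocrine therapy outcome will be adherence to endocrine therapy assessed via the electronic medical records". It gives no threshold for nonadherence on that measure and no rule for recurrence or death.

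A list then opens with "Secondary assessments of endocrine therapy will be" and covers urinary AI level and three self-report questions about the past month. Directly after those questions comes the rule at issue: "Participants who report that they have discontinued taking tamoxifen or AI will also be classified as nonadherent to endocrine therapy". For women lost to follow-up, item 12 turns to prescription refill data.

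Item 3(c), Adherence to Endocrine Therapy, contains the only exception: "If women switch AIs or from AI to tamoxifen, we will capture this, but classify them as having continued endocrine therapy and therefore adherent". The same section says that women who stop will "be asked to indicate their rationale(s) via an interview-administered questionnaire". The Medical Usage paragraph lists the 5-year record abstraction: "breast cancer recurrence, second primary breast cancer, weight, health care utilization". Item 3(a) adds mortality. No sentence uses the reasons, the disease events or the deaths in scoring adherence.

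On timing, item 12 says "The outcome of endocrine therapy adherence will be assessed at the 2 and 5-year follow ups", whereas Aim 1b reads "Adherence to endocrine therapy in women taking tamoxifen or Aromatase Inhibitors (AIs) at 12- and 24-months after enrollment".

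**The concern.** The outcome is meant to show whether women keep taking a drug that is prescribed to them. Once recurrence or a second primary cancer has led to the drug being withdrawn, not taking it is no longer a failure to follow the prescription. The rule nevertheless records it as one, so the self-report measure mixes behaviour with disease events.

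If such events are equally common in both arms, the difference in adherence is diluted. If they differ, part of the disease difference is reported as an adherence effect. The second case cannot be dismissed, because the Summary and Significance text offers better prognosis as a possible benefit of early lifestyle change, and item 1 lists recurrence as an exploratory endpoint. The longer the follow-up, the more such stops there can be, so the 5-year assessment is the more exposed.

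**Working it through.** **Reading the rule.** Take a woman who takes her AI fully for three years. The cancer recurs, the AI is stopped, and she reports this at 5 years.

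- Item 12: she reports discontinuation, so she is nonadherent.
- Item 3(c), switch exception: it helps her only if the replacement is another AI or tamoxifen.
- Item 3(c), reasons for stopping: recorded, but not used in the classification.
- Items 3(a) and 3(c), recurrence: abstracted, but not linked to adherence.

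She therefore stays nonadherent on the self-report measure. On the EMR measure her classification is undefined.

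**The plan's own figure.** Inputs from item 12, Power and Sample Size: 50% vs 75%, two-sided 0.05, 90% power, 76 per group. With p̄ = 0.625:

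n = [1.96·√(2p̄(1−p̄)) + 1.2816·√(p₁(1−p₁)+p₂(1−p₂))]² / (p₂−p₁)² = (1.3419 + 0.8477)² / 0.0625 = 76.7, so 77 per group against 76 stated. Power at 76 per group is 89.7%. The figure reproduces.

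**Illustration.** The plan expects about 120 women on endocrine therapy (70% of 172), or 60 per arm at 1:1. Let d be the share of women whose drug is stopped by a disease event, equal by arm and independent of adherence. The documents give no d, so 2% to 10% is assumed. Under the rule, observed adherence is true adherence × (1 − d), and

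power = Φ{[(p₂−p₁)√n − 1.96·√(2p̄(1−p̄))] / √(p₁(1−p₁)+p₂(1−p₂))}.

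At d = 0 this is Φ[(1.9365 − 1.3419)/0.6614] = Φ(0.899) = 81.6%. Women moved from adherent to nonadherent = 120 × d × 0.625, where 0.625 is the mean of 50% and 75%. The last column leaves the affected women out, with 60 × (1 − d) per arm at 50% vs 75%.

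| d | Observed rates | Difference (points) | Women moved | Power, rule applied | Power, women left out |
|---|---|---|---|---|---|
| 0% | 50.0% vs 75.0% | 25.0 | 0 | 81.6% | 81.6% |
| 2% | 49.0% vs 73.5% | 24.5 | 1.5 | 79.4% | 80.8% |
| 5% | 47.5% vs 71.3% | 23.8 | 3.8 | 76.1% | 79.5% |
| 10% | 45.0% vs 67.5% | 22.5 | 7.5 | 70.5% | 77.3% |

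**Unequal events.** Let true adherence be 50% in both arms and assume d = 10% in usual care and 5% with intervention. The rule gives 45.0% vs 47.5%, a spurious 2.5 points in favour of the intervention. At 60 per arm the two-sided rejection probability is Φ(−1.686) + Φ(−2.235) = 0.046 + 0.013, about 6% instead of 5%.

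**The case against.** Three stronger readings are tempting, and the documents do not support them.

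- **Deaths are scored as nonadherent.** The rule covers women who report stopping, and a woman who has died reports nothing. The refill fallback is for loss to follow-up, and nothing says that an absent refill after death counts as failure. The plan is silent on deaths.
- **The primary endocrine outcome is contaminated.** The rule follows the heading for secondary assessments and comes straight after the self-report items, while the primary measure is the EMR. On the other side, the rule speaks of nonadherence to endocrine therapy in general, and the EMR measure has no rule of its own. Its scope is open, which calls for clarification but does not show that the primary result is affected.
- **The trial loses a known amount of power at 5 years.** The event rates are assumed. The 50% control rate is the plan's assumption for one year after starting the drug. The 5-year follow-up includes only women who agreed to recontact and then take part, so 60 per arm at 5 years has no support.

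It can also be argued that counting every stop as failure is a legitimate composite, since the background section treats early discontinuation as an outcome in itself. That is fair if the plan declares the choice, and it is a reason to keep that version as a sensitivity analysis. The plan does not declare it, and it collects reasons without saying what they are for. Finally, the effect is small where events are few: at an assumed 2%, it is half a percentage point and one or two women.

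What remains is a written rule that gives the wrong classification for an identifiable group of women.

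**Conclusion.** The point holds in limited form. As written, a self-reported stop caused by recurrence or a second primary breast cancer is scored as an adherence failure unless the woman moved to another AI or tamoxifen. This follows from the text and needs no assumption. Whether the same scoring reaches the primary EMR outcome, and how deaths are treated in either measure, is not stated.

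The size cannot be fixed from the documents. If the rule applied to the tested outcome, power would fall from about 82% to about 79% at an assumed 2% event rate and about 71% at 10%. This rests on 60 women per arm, 50% vs 75% adherence, and events equal by arm and independent of adherence. If events cluster in women who are already nonadherent, the dilution is smaller. The possible false difference between arms is also modest under the rates tried. The matter is mainly one for 5 years. It would weigh less if the 12- and 24-month timing in Aim 1b governs, and the plan should reconcile that timing with item 12.

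**What to change.** Amend the rule in item 12, before outcomes are classified, as follows:

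- A reported discontinuation is not scored as nonadherence when the rationale interview or the record abstraction shows that it followed recurrence or a second primary breast cancer.
- For the EMR outcome, adherence is scored up to the date of that event or of death. The plan should also state what counts as nonadherence in the EMR and whether the discontinuation rule applies to it.
- For the past-month self-report items, the woman is treated as not assessable after the event, because those items cannot be scored back to an earlier date.
- The version counting all stops as nonadherence is reported as a sensitivity analysis.

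The cost is a few sentences in the analysis plan and an event date on the record-abstraction forms. Reasons for stopping, recurrence, second primary cancer and mortality are already to be collected. The drawback is that a few women have a shortened or missing assessment defined by an event after randomization, so their number should be reported by arm. Leaving women out also costs some power: in the illustration it is 80.8% at a 2% event rate and 77.3% at 10%, still above the figures with the rule applied. The amendment changes only how stops are classified in the analysis, not how any patient is managed.

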a) **Experimental Design:** The proposed study is a randomized trial evaluating the impact of a dietary and physical activity guidelines intervention vs. usual care on adherence to breast cancer treatments, body composition, and changes in biomarkers in 172 women newly diagnosed with breast cancer who will receive neoadjuvant or adjuvant chemotherapy as part of their treatment. The intervention will be conducted in person in the breast clinic at Smilow Cancer Hospital/Smilow Care Center and/or via telephone/video over one-year. When possible, assessments (4 in total) will be completed at a study baseline clinic visit (after diagnosis for women receiving neoadjuvant chemotherapy and after breast surgery for women receiving adjuvant chemotherapy, but prior to the second chemotherapy infusion) and post chemotherapy, at 1- and 2-yrs post-diagnosis. If not possible for a patient to travel to New Haven for the in-person study assessments, the patient will complete online or/and hard copy study questionnaires. These may be administered by phone. The assessments conducted at the in-person visit are optional at all timepoints. The assessments include: physical exam (height, weight, waist and hip circumference), DXA scan, blood and urine collection, grip strength and carotenoid assessment. Following publication of the initial primary results the manuscript will be mailed to all study participants. Participants who consented to be recontacted will be asked if they are willing to participate in a 5-year follow. Five-year follow up will include assessment of dietary intake, physical activity, and quality of life, similar to these 1- and 2-year assessments. Data regarding breast cancer recurrence, mortality and medical usage will be abstracted from the EMR.

Study Population: We will enroll 172 women over 2.5 years (~ 8-9 women/month). Women will be enrolled prior to their the second neoadjuvant or adjuvant chemotherapy session. Given treatments are often of a longer duration for stage IV (which includes recurrent breast cancer) breast cancer, women with stage IV will not be eligible. Patients with recurrent cancer, independent of whether they have received chemotherapy at the time of initial diagnosis, or the time that has elapsed since the initial diagnosis, are eligible. The treatment of the recurrent cancer must be intended to be curative.

Table 1. Eligibility Criteria

Inclusion Criteria:

- Diagnosed with Stage I-III breast cancer

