Women will be asked to complete the self-administered study questionnaires prior to the in-person baseline visit. They will be provided a link via email to the online questionnaires or given a hard copy version if preferred.

Assessments	Screening	Baseline	Post-chemo	1-year	2-year	5-year
Screening Questionnaire	X					
Demographic Questionnaire*		X				
Medical History Questionnaire*		X				
Food Frequency Questionnaire		X	X	X	X	X

Phone assessment 24-hour dietary recall – 1-day ^{&1}		X	X	X	X	
Physical Activity Questionnaire		X	X	X	X	X
Patient Global Assessment (SGPGA)	X					
PROMIS quality of life questionnaires(74)		X	X	X	X	X
Prescription Medication		X	X	X	X	X
Adherence to medication questionnaire(75, 76)				X	X	X
Neuropathy – EORTLC QLQ-CIPN20(77)		X	X	X	X	X
Work history			X	X	X	X
Beliefs about Medication Questionnaire(78)				X	X	X
Treatment Satisfaction Questionnaire for Medication(79)				X	X	X
Health Insurance, prescription coverage and prescription refill habits				X	X	X
Medication usage questionnaire				X	X	X
Aromatase Inhibitor/Tamoxifen usage form				X	X	X
Breast Cancer Prevention Trial (BCPT) Symptom Scales (80)		X	X	X	X	X
Brief Pain Index		X	X	X	X	X
Homunculus		X	X	X	X	X
Y5-Lymphedema Questionnaire						X
Supplement intake/over the counter medication *		X	X	X	X	X
Y1 -Lymphedema Questionnaire				X		
Y2- Lymphedema Questionnaire					X	
Satisfaction Questionnaire (Intervention group)				X		
Side-effects and toxicity assessment (PRO-CTCAE™)		X	X			
Chemotherapy delay/dose reduction/reasons (extracted from EPIC EMR)			X			
Grip Strength [%]		X	X	X	X	
EPIC 2YR follow up treatment form					X	

EPIC 5 Year medical usage and breast cancer status abstraction						X
Two Year Follow up Treatment form'					X	
Height and weight measured [%]		X	X	X	X	
Waist and hip circumference measured [%]		X	X	X	X	
Blood collection [%]		X	X	X	X	
DXA scan [%]		X	X	X	X	
Urine collection ^{%@}				X	X	
Urine collection for pregnancy test if applicable prior to DEXA [%]		X	X	X	X	
Stool collection [%]		X	X	X		
Skin carotenoids [%]		X	X	X	X	

*: Part of the Baseline Questionnaire

%: Applicable only to the Yale site when in-person visits are completed. Assessments are optional.

@ Applicable to women who are prescribed an aromatase inhibitor

&: Assessment is optional.

1: Discontinued in August 2020.

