Note: As of mid-March 2020, in-person visits and associated in-person assessments (DXA, blood and urine collection, weight/height and waist hip measurements, skin carotenoids, stool collection, grip strength) could no longer be conducted due to the coronavirus pandemic. In-person visits and assessment will re-start when allowed by the institution.

Screening Questionnaire: Eligibility criteria will be determined from electronic medical records via EPIC and/or via interview-administered questionnaire during the screening visit.

Screening will include determining eligibility on diet and physical activity by asking the following questions:

1. 'Prior to your diagnosis of breast cancer, did you exercise, *(for example, jogging, walking on a treadmill or stationary bicycling)?'

If the patient reports exercising less than 150min/wk moderate aerobic exercise and less than 75 min/wk of vigorous aerobic exercise (e.g. running) or an equivalent combination they are coded 'no' on the exercise criteria

- 2a. 'Prior to your diagnosis of breast cancer, how many servings of vegetables did you usually eat per day (don't include French fries)?'
- 2b. 'Prior to your diagnosis of breast cancer, how many servings of fruit did you usually eat per day?'

A card describing serving sizes will be provided for the patient's reference.

Eligibility Criteria for fruit and vegetable intake: < 7 fruit and vegetables combined per day
If the patient reports eating less than 7 fruits and vegetables per day, they are coded 'no' on the healthy eating criteria

To be eligible, participants need to respond 'No' to both questions.

These two guidelines have been used as screening criteria in other diet and physical activity trials. (81, 82)

In addition, we will administer the Patient-Generated Subjective Global Assessment (PG-SGA) (83). If malnourished a patient will be ineligible for the study.

All patients who are screened by phone following receipt of MD consent to contact and who are ineligible for the study or do not wish to participate in the LEANer study, will be asked if they would be willing to be contacted about participation in future studies.

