1. The entire consent form will be reviewed in detail with the subject in a private, one-on-one setting at the first intake appointment. The intake appointment may be a visit separate to the baseline HRU visit or may be combined with the baseline HRU visit. All risks and potential benefits will be described. Any questions the subject may have will be addressed. If the subject wishes, she may take the consent form home and consider it further before signing. Subjects may also request to speak to anyone on the research team about questions they have or to consult others, including their physician and family members. Once the subject has signed the consent, she may withdraw consent at any time. Informed consent must be obtained prior to performance of any protocol specific procedures. A copy of the consent will be provided to the participant.

OR

2. When a subject is unable to travel to meet with study personnel prior to the second chemotherapy session (enrollment must be prior to this timepoint) the subject will be offered participation in the study without the requirement of in-person visits to the Hospital Research Unit at Yale New Haven Hospital. This may occur when patients for example when patients from Torrington or Lawrence and Memorial

(New London) care centers, Columbia University or DFCI wish to enroll in the study. Except for DFCI patients, informed consent will not be obtained in-person but verbal agreement to participate will be obtained with use of the information sheet – see the study information sheet. The information sheet will be reviewed in detail with the subject by phone. All risks and potential benefits will be described. Any questions the subject may have will be addressed. If the subject wishes, she can request that a copy of the information sheet be mailed or emailed to her before she decides whether to participate. Subjects may also request to speak to anyone on the research team about questions they have or to consult others, including their physician and family members. Once the subject has verbally consented to participate in the study, she may withdraw from the study at any time. A copy of the information sheet will be provided to the participant. If an enrolled subject decides that she wishes to complete the later in-person study assessments (post-chemo, 1-year or 2-year) they will be asked to complete in-person consent will be obtained using the study consent form.

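### For secondary outcomes measured in person at Yale, the change-from-baseline model discards all follow-up data from any woman without a baseline measurement

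*Combined protocol and SAP*

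**What the plan says.** Item 12 of Section I (Statistical Considerations) sets one model for the secondary aims, a mixed model for repeated measures combined with analysis of covariance. The response is each woman's follow-up value minus her baseline, and this difference "will be modeled as a function of treatment and time with a covariate included for the baseline value". The missing-data paragraph in the same item assumes data are missing at random and explains this in terms of loss to follow-up. It promises to evaluate the impact of missing data, but names no imputation and no handling of a missing baseline.

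Other sections determine who has a baseline:

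- Section I, 3(a), Experimental Design: "The assessments conducted at the in-person visit are optional at all timepoints".
- Section I, 3(c), footnote to the assessment table, for blood, DXA, height and weight, skin carotenoids and other in-person measures: "Applicable only to the Yale site when in-person visits are completed. Assessments are optional".
- Section I, 3(c), Note: from mid-March 2020 these assessments "could no longer be conducted due to the coronavirus pandemic". It adds: "In-person visits and assessment will re-start when allowed by the institution".
- Section III, item 6, Process of Consent/Assent, provides in-person consent for women first enrolled remotely. The provision begins: "If an enrolled subject decides that she wishes to complete the later in-person study assessments (post-chemo, 1-year or 2-year".

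**The concern.** Baseline enters the model twice, in the response and as a covariate. A repeated-measures model tolerates a missing follow-up visit, but it cannot use a woman whose baseline is absent. All her later values go, even if she has post-chemotherapy, 1-year and 2-year measurements.

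A missed baseline cannot be made up, because the baseline visit has to precede the second infusion. The protocol nevertheless expects some women to miss it and still attend later. At stake is the precision of the arm comparisons for biomarkers (Aim 2a), body composition (Aim 2b) and the change in skin carotenoids (Aim 4b).

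**Working it through.** **Can such women exist?** Three routes are written into the protocol:

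1. A Yale participant declines the optional baseline test and accepts a later one.
2. A woman enrols remotely and chooses in-person visits later, for which Section III, item 6 provides consent.
3. A woman enrols during the pause and attends after the restart. Section I, 3(b) describes screening procedures for the period of remote working, so recruitment during that time was foreseen.

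**Which outcomes are exposed?** Those that are measured in person at Yale and analysed as change: insulin, CRP, NCS1, weight and BMI, DXA measures and skin carotenoids. The following are largely or wholly unaffected:

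- Quality-of-life questionnaires can be completed online, on paper or by phone.
- pCR is not a change score.
- For stool, women randomized after their first infusion give no sample at baseline or later.
- The primary endpoints do not use this model.
- Dana-Farber participants have no in-person assessments, so they are absent under any model.

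**Size of the loss.** Let f be the fraction without a baseline among women with a given follow-up value, and r the baseline/follow-up correlation. Neither is in the documents, so both are assumed. Take one follow-up visit, equal arms, unit variance and a baseline mean common to both arms. Information on the arm contrast, per woman with follow-up, is then:

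- planned model: (1 − f)/(1 − r²)
- baseline as a response: (1 − f)/(1 − r²) + f

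The relative gain is g = f(1 − r²)/(1 − f), and the standard error falls by 1 − 1/√(1 + g).

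| f | r | g | Fall in SE |
|---|---|---|---|
| 10% | 0.5 | 0.10 × 0.75/0.90 = 8.3% | 3.9% |
| 10% | 0.7 | 0.10 × 0.51/0.90 = 5.7% | 2.7% |
| 10% | 0.8 | 0.10 × 0.36/0.90 = 4.0% | 1.9% |
| 20% | 0.5 | 0.20 × 0.75/0.80 = 18.8% | 8.2% |
| 20% | 0.7 | 0.20 × 0.51/0.80 = 12.8% | 5.8% |
| 20% | 0.8 | 0.20 × 0.36/0.80 = 9.0% | 4.2% |
| 30% | 0.5 | 0.30 × 0.75/0.70 = 32.1% | 13.0% |
| 30% | 0.7 | 0.30 × 0.51/0.70 = 21.9% | 9.4% |
| 30% | 0.8 | 0.30 × 0.36/0.70 = 15.4% | 6.9% |

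**Illustration with insulin.** The sample-size text gives a difference of 3.0 µU/mL, an SD of 8.0 and 112 per group, without stating power. The figure reproduces at 80% power and two-sided 0.05: 2 × (1.960 + 0.842)² × 8²/3² = 111.6, rounded up to 112.

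The Yale target is 133 (Section III, item 1), or 66.5 per arm. With the same inputs, power there is Φ(3/(8√(2/66.5)) − 1.960) = 0.58. That fall from 0.80 comes from the number of women and owes nothing to the choice of model.

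The model's own share can be shown by replacing 66.5 with 66.5(1 − f) for the planned model, and with 66.5(1 − f)(1 + g) for the alternative. This treats 8.0 as the SD after baseline adjustment and supposes that every Yale participant has the follow-up value.

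| f | Planned model | Baseline as a response, r = 0.8 to 0.5 |
|---|---|---|
| 10% | 0.54 | 0.55–0.57 |
| 20% | 0.49 | 0.52–0.56 |
| 30% | 0.44 | 0.49–0.55 |

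**The case against.** Baseline-adjusted change in a repeated-measures model is a standard analysis, and it keeps women who have a baseline and only some follow-up visits. The affected group may be small. A woman counts only if she missed the baseline test and later attended at Yale, and those who missed it because of travel or reluctance may miss later visits too. Nothing in the documents supports a particular f, and the 13% figure pairs the largest assumed f with the lowest assumed r. The plan does not rule out imputing a baseline. All of this stands, and it limits the size of the point. The fact remains that the model as written cannot use these women's data, and that no other provision recovers them.

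Three stronger readings are tempting:

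- A reader might infer a breach of intention to treat. The plan's sentence says that randomized women are grouped by assigned arm regardless of compliance. It does not promise that each woman contributes to every in-person measure, and no model could deliver that here.
- A reader might infer bias between arms. A missing baseline largely reflects the enrolment route or the institutional pause. Among women with a baseline the randomized comparison would then ordinarily remain fair. The documents do not say whether the baseline visit always precedes randomization, so this is not certain, but no bias is shown.
- A reader might infer a conflict with the missing-at-random assumption. That text concerns loss to follow-up and leaves a missing baseline unaddressed.

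**Conclusion.** The point holds for the Yale in-person secondary outcomes analysed as change. Follow-up values that the protocol allows to be collected would be discarded by the planned model. The cost is precision: a standard error about 2–13% larger than it need be, expressed as the reduction available, for assumed f of 10–30% and r of 0.5–0.8. If f is near zero the cost is negligible, and the study team can settle this by counting. The change is worth making because the method is available and needs no new data. It does not call the primary endpoints or the validity of the arm comparison into question.

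**What to change.** For these outcomes, replace the change-score model with a constrained longitudinal model. Baseline and all follow-up values are responses, with an unstructured covariance matrix and terms for visit and arm by visit. Arm means are constrained to be equal at baseline, which randomization justifies. Report the same contrasts at each follow-up visit. With a common baseline mean, the arm difference in change equals the arm difference at that visit, so Aim 4b keeps its target. Report by arm how many women have follow-up without a baseline.

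The cost is a revised paragraph and a different model statement in the SAS software already planned. The small downside is reliance on missing at random for absent baselines. The planned change-score model can stay as a sensitivity analysis. Prespecified multiple imputation of baseline is a workable alternative.
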